Appendix 1. Relevant ICD-9/10-CM code and procedure code

	ICD9	ICD10
For inclusion criteria		
COPD	491.x, 492.x, 496	J41.x, J42, J43.x, J44.x
For exclusion criteria		
Asthma	493.x	J45.x
Allergic rhinitis	477.x	J30.x
Lung cancer	162.x	C33.x, C34.x, C7A.090,
		D02.2
Interstitial lung disease	238.1, 500, 501, 502, 503,	J60, J61, J62.x, J63.x, J64,
	504, 505, 506.4, 508.1,	J65, J66.x, J68.4, J70.x (no
	508.8, 515, 516.x	70.2), J84.1x (no J84.114),
		J84.2, J84.3, J84.89, J84.9,
		J94.1

Procedure codes	Content
68037A	Lung transplantation
68037B	Lung transplantation - Unilateral lung
68047B	Lung transplantation - bilateral sequential or en bloc double lung

Statistical and Epidemiological Analysis Plan (SEAP) for Non-Interventional Studies (NIS) Template

c40431892-01 Page 29 of 38

Proprietary confidential information © 2022 Boehringer Ingelheim International GmbH or one or more of its affiliated companies

Appendix 2. List of COPD medication

Groups	Drug name	ATC code
LAMA	Tiotropium bromide	R03BB04
	Glycopyrrolate	R03BB06
	Umeclidinium	R03BB07
LABA	Salmeterol	R03AC12
	Formoterol	R03AC13
	Procaterol	R03AC16
	Indacaterol	R03AC18
	Olodaterol	R03AC19
ICS	Beclometasone(=beclomethasone)	R03BA01
	Budesonide	R03BA02
	Fluticasone	R03BA05
	Ciclesonide	R03BA08
ICS/LABA	Salmeterol and Fluticasone	R03AK06
	Formoterol and Budesonide	R03AK07
	Formoterol and Beclometasone	R03AK08
	Vilanterol and Fluticasone furoate	R03AK10
	Formoterol and Fluticasone	R03AK11
LABA/LAMA	Vilanterol and Umeclidinium bromide	R03AL03
	Indacaterol and Glycopyrronium bromide	R03AL04
	Olodaterol and Tiotropium bromide	R03AL06
LABA/LAMA/ICS	Vilanterol, Umeclidinium bromide and Fluticasone furoate	R03AL08
	Formoterol, Glycopyrronium bromide and Beclometasone	R03AL09

Statistical and Epidemiological Analysis Plan (SEAP) for Non-Interventional Studies (NIS) Template c40431892-01 Page 30 of 38

Proprietary confidential information © 2022 Boehringer Ingelheim International GmbH or one or more of its affiliated companies

Appendix 3. ICD codes and operational definition of adverse events

	Adverse events	ICD codes	Operational definition
1	Nasopharyngitis	ICD9: 472.2, 460 ICD10: J31.1, J00	Inpatient or outpatient (including ER visit) diagnosis.
2	Pneumonia	ICD9: 480-486, 487.0 ICD10: J10.0, J11.0, J12- J18,	 Primary inpatient diagnosis Inpatient diagnosis.
3	Moderate COPD exacerbation	ICD9: 491.x, 492.x, 496 ICD10: J41.x, J42, J43.x, J44.x	Outpatient diagnosis plus a prescription for oral corticosteroid or antibiotic for respiratory infection
4	Severe COPD exacerbation	ICD9: 491.x, 492.x, 496 ICD10: J41.x, J42, J43.x, J44.x	Inpatient or ER visits with a primary diagnosis.
5	Arrhythmia	ICD9: 427.x ICD10: I47.x, I48.x, I49.x	Inpatient or outpatient (including ER visit) diagnosis.
6	Myocardial ischemia	ICD9: 410.x, 411.x, 413.x ICD10: I20.x, I21.x, I22.x, I23.x, I24.x	Inpatient or outpatient (including ER visit) diagnosis.
7	Supraventricular tachycardia	ICD9: 427.0 ICD10: I47.1	Inpatient or outpatient (including ER visit) diagnosis.
8	Constipation	ICD9: 564.0, 564.00, 564.09 ICD10: K59.0, K59.00, K59.09	Inpatient or outpatient (including ER visit) diagnosis.
9	Diarrhoea	ICD9: 787.91 ICD10: R19.7	Inpatient or outpatient (including ER visit) diagnosis.
10	Urinary retention	ICD9: 788.2, 788.20, 788.29 ICD10: R33.x	Inpatient or outpatient (including ER visit) diagnosis.
11	Urinary tract infection	ICD9: 590, 595, 601, 604 ICD10: N10, N12, N15.1, N30.0, N30.8, N30.9, N41.0, N41.2, N41.3, N39.0	 Primary inpatient diagnosis Inpatient diagnosis. Either inpatient diagnosis or at least 2 outpatients (including ER visit) diagnosis; diagnostic interval within 30 days.
12	Urticaria	ICD9: 708.x ICD10: L50.x	Inpatient or outpatient (including ER visit) diagnosis.
13	Rash	ICD9: 782.1 ICD10: R21	Inpatient or outpatient (including ER visit) diagnosis.

Statistical and Epidemiological Analysis Plan (SEAP) for Non-Interventional Studies (NIS) Template

c40431892-01 Page 31 of 38

14	Glaucoma	ICD9: 365.x	Inpatient or outpatient
		ICD10: H40.x	(including ER visit) diagnosis
			from ophthalmologist.
15	Nonfatal myocardial	ICD9: 410.x, 411.x	1. Primary inpatient diagnosis
	infarction	ICD10: I21.x, I22.x, I23.x	+ hospital discharge
			without death certificates
			2. Inpatient diagnosis +
			hospital discharge without
			death certificates
16	Nonfatal hemorrhagic stroke	ICD9: 430, 431, 432.x	1. Primary inpatient diagnosis
		ICD10: 160.x, 161.x, 162.x	+ hospital discharge
			without death certificates
			2. Inpatient diagnosis +
			hospital discharge without
			death certificates
17	Nonfatal ischemic stroke	ICD9: 433.x, 434.x	1. Primary inpatient diagnosis
		ICD10: 163.x, 166.x	+ hospital discharge
			without death certificates
			2. Inpatient diagnosis +
			hospital discharge without
			death certificates
18	Nonfatal acute	ICD9: 436	1. Primary inpatient diagnosis
	cerebrovascular disease	ICD10: 167.8	+ hospital discharge
			without death certificates
			2. Inpatient diagnosis +
			hospital discharge without
			death certificates
19	Fatal events		All cause of death

Statistical and Epidemiological Analysis Plan (SEAP) for Non-Interventional Studies (NIS) Template c40431892-01 Page 32 of 38

Proprietary confidential information © 2022 Boehringer Ingelheim International GmbH or one or more of its affiliated companies

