6.2 SETTING

Data used in this study will come from the Taiwan National Health Insurance (NHI) claims data. Cohort for incident Tio/Olo combined inhaler use would be identified from 2014 through 2019, with a 1-year look-back period to define new user. Cohort for other incident LAMA/LABAs combined inhaler use would be identified from 2014 through 2019, and also with a 1-year look-back period to define new user.

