8. DATA SOURCES

Data sources include Taiwan National Health Insurance (NHI), Taiwan Cancer Registry (TCR) and Taiwan Mortality Data. Taiwan Department of Statistics, Ministry of Health and Welfare is the unit designated by the government to manage health and social welfare statistical databases, and to develop data platform for academic research. Through the services provided by the Health and Welfare Data Science Center (HWDSC) of the Department of Statistics, researchers may access a wide range of health and welfare data, including claims, mortality (with cause of death) and Taiwan Cancer Registry (TCR). The HWDSC staff encrypt the national ID for all individuals according to a secure encryption algorithm that is not made known to the public. The encrypted ID is unique for all individuals and will be used for linkage between databases.

The ICD-9-CM coding system was used until the end of 2015 and the use of ICD-10-CM codes started on January 1, 2016.

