Appendix 4. ICD codes and operational definition of comorbidities

	Comorbidities:	ICD codes	Operational definition
1.	Diabetes	ICD9: 250	Either inpatient diagnosis or
		ICD10: E10.x-E11.x	more than twice outpatient
			diagnosis
2.	Cardiovascular disease	ICD9: 250.7, 401-405,	Either inpatient diagnosis or
		410-414, 425-428, 429.1-	more than twice outpatient
		429.3, 441, 442, 458	diagnosis
		ICD10: E10.5x, E11.5x,	
		I10-I13.x, I15.x, I20.x-	
		122.x, 124.x, 125.x, 142.x-	
		144, 145.xx, 146.x-149.x,	
		I50.xx, I51.5, I51.7, I51.9,	
		171.xx, 179.0, 172.x,	
		177.7x, 195.x	
3.	Cerebrovascular disease	ICD9: 430-438	Either inpatient diagnosis or
			more than twice outpatient
		166.x, G45.x, G46.x, 167.x-	diagnosis
		169.x	
4.	Cancer	ICD9: 140-199, 200-208	Inpatient diagnosis.
		ICD10: C00-C26, C30-34,	
		C37-39, C40-41, C43-49,	
		C4A, C50-58, C60-69,	
		C70-79,C7A, C7B, C80-	
		86, C88, C90-96,	
5.	Chronic kidney disease	ICD9: 585-587,	Either inpatient diagnosis or
		ICD10: N18-19, N26.1,	more than twice outpatient
		N26.9	diagnosis
6.	Pneumonia	ICD9: 480-486, 487.0	Inpatient diagnosis
		ICD10: J10.0, J11.0, J12-	
		J18,	
7.	Cirrhosis		Either inpatient diagnosis or
		ICD10: K70.3x, K74.3,	more than twice outpatient
		K74.4, K74.5, K74.6x	diagnosis

Statistical and Epidemiological Analysis Plan (SEAP) for Non-Interventional Studies (NIS) Template

c40431892-01 Page 33 of 38

Proprietary confidential information © 2022 Boehringer Ingelheim International GmbH or one or more of its affiliated companies

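### The arrhythmia code list appears narrower in ICD-10 than in ICD-9, so this one outcome seems to change definition on 1 January 2016

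*SAP*

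**What the plan says.** SAP section 7.2.1 lists arrhythmia among the primary adverse events and groups it with the chronic conditions. A subject with the diagnosis in the one-year baseline is removed from the analysis of that event. The codes are in Appendix 3, row 5: "ICD9: 427.x ICD10: I47.x, I48.x, I49.x". The ICD-9 side is the whole category with nothing carved out. Row 7, supraventricular tachycardia, pairs one specific code with another: "ICD9: 427.0 ICD10: I47.1".

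Appendix 4 defines the cardiovascular comorbidity. Its ICD-9 side contains "410-414, 425-428, 429.1", so all of 427 is in. Its ICD-10 side contains "144, 145.xx, 146.x-149.x". The leading 1 is the letter I misread in text extraction, so this run includes I46.x to I49.x.

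SAP section 8 dates the change of coding: "The ICD-9-CM coding system was used until the end of 2015 and the use of ICD-10-CM codes started on January 1, 2016". SAP section 6.2 sets the cohort period: "Cohort for incident Tio/Olo combined inhaler use would be identified from 2014 through 2019". Table 2 of SAP Annex 1 reports one arrhythmia rate for the whole period.

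**The concern.** The two halves of the arrhythmia row apply to different calendar years of one pooled rate. Events up to the end of 2015 are found with all of 427.x, and later events with I47-I49 only. If part of 427.x corresponds to I46, those diagnoses count before the switch and not after it. The arrhythmia rate could then drop in 2016 because of coding alone.

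The same row decides who is at risk. A patient who enters in 2016 has a baseline year partly in ICD-9 but outcomes only in ICD-10. A patient who enters in 2015 and is still on treatment in 2016 has an ICD-9 baseline and some ICD-10 follow-up. For these patients the exclusion uses the wider list and the later outcome the narrower one.

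Arrhythmia is also one of only four events in the precision table of Protocol section 9.5, so the sponsor treats it as a leading safety outcome.

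**Working it through.** **1. The two appendices side by side**

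| Place | ICD-9 side | ICD-10 side |
|---|---|---|
| Appendix 3, arrhythmia | 427.x, no exception | I47.x, I48.x, I49.x |
| Appendix 4, cardiovascular disease | 425-428 (among others) | a run that includes I46.x-I49.x (among others) |

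I46 appears in the list that covers all of 427 and is absent from the arrhythmia row. The readable text gives no reason for the difference.

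**2. The plan's own figure**

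Protocol section 9.5 gives 1.82 per 100 patient-years, N = 4000, uniform entry over 0 to 6 years, and a 95% interval of 1.583 to 2.067.
- Person-years = 4000 × 3 = 12,000.
- Expected events = 0.0182 × 12,000 = 218.4.
- The 2.5% and 97.5% quantiles of Poisson(218.4), divided by 12,000, give 1.583 and 2.067, an exact match.
- Half-width = (2.067 − 1.583)/2 = 0.242, which is 13% of the rate.

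**3. Share of person-time in the ICD-9 years (2014-2015)**

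Entry is uniform over 6 years, at 4000/6 = 667 per year.
- All followed to the end of 2019: 667 × 2²/2 = 1,333 of 12,000, or 11.1%.
- Follow-up of D years on drug, for D up to 2: share = (2D − D²/2)/(6D − D²/2). For D = 1 this is 1.5/5.5 = 27.3%. For D = 0.25 it is 0.469/1.469 = 31.9%. As D approaches 0 it tends to 2/6 = 33.3%.

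The SAP ends follow-up at a 45-day lapse without a prescription, so the shorter durations are relevant. SAP section 9.3 mentions years in which the product was not covered but does not name them. If they fall early in the period, the ICD-9 share is smaller.

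**4. Effect on the rate**

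Let c be the share of 427.x events that would be coded I46 after the switch (not in the documents, so assumed) and s the ICD-9 share of person-time. Take 1.82 as the rate under the full definition. Then:
- rate from 2016 = 1.82 × (1 − c);
- fall in the pooled rate = 1.82 × c × (1 − s).

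| c (assumed) | Rate from 2016 | Pooled rate, s = 1/9 | Pooled rate, s = 1/3 | Events lost of 218.4 |
|---|---|---|---|---|
| 0.5% | 1.811 | 1.812 | 1.814 | 0.7-1.0 |
| 1% | 1.802 | 1.804 | 1.808 | 1.5-1.9 |
| 2% | 1.784 | 1.788 | 1.796 | 2.9-3.9 |
| 5% | 1.729 | 1.739 | 1.759 | 7.3-9.7 |
| 10% | 1.638 | 1.658 | 1.699 | 14.6-19.4 |

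The smallest fall is 1.82 × 0.005 × 2/3 = 0.006 and the largest is 1.82 × 0.10 × 8/9 = 0.162 per 100 patient-years. Both lie inside the half-width of 0.242. The table does not model the baseline exclusion, whose effect cannot be sized from the documents.

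**The case against.** **The inference is indirect.** Appendix 4 describes a broad comorbidity and does not say which of 425, 426, 427 or 428 corresponds to I46. A broad baseline condition may also include a category that a narrower outcome leaves out on purpose. This stands in part: the documents hold no crosswalk, so the mismatch is apparent and not proven. But if the omission is deliberate, the ICD-9 side should have a matching exception. It has none, although the supraventricular tachycardia row shows that the SAP uses subcodes when it means to.

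**The effect is small and the analysis is descriptive.** This also stands. The comparison between cohorts covers baseline characteristics only, and its comorbidities come from Appendix 4, so it is not touched.

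**A check by calendar period may exist.** The protocol's checklist places stratified and sensitivity analyses in section 9.7.2. That section and SAP section 10.2 are not in the available text, so nobody can say from these documents that no such check is planned.

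**Two stronger readings are tempting and not supported.**
- A reader might infer that ischemic stroke changes definition too, because "ICD9: 433.x, 434.x" is paired with "ICD10: 163.x, 166.x" (again with 1 for I), which skips a number. A gap in numbering does not show a gap in content. The documents give no code titles, and the start of the ICD-10 cell for cerebrovascular disease in Appendix 4 was lost in extraction, so there is nothing to compare with.
- A reader might take 11% as the ICD-9 share, or count all 2014-2016 entrants as affected by mixed definitions. The 11% holds only if everyone is followed to the end of 2019. Patients who enter in 2014 or 2015 and stop before 2016 have baseline and follow-up both in ICD-9.

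**Conclusion.** The point holds as a minor one for arrhythmia alone. As written, the definition appears narrower from 1 January 2016, so the pooled rate mixes two definitions, and patients who cross the switch have an exclusion rule and an outcome that differ. The likely direction is an equal or lower rate from 2016.

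The ICD-9 years hold about 11% to 33% of person-time under uniform entry, or less if the product was not covered early in the period. For an assumed unmatched share of 0.5-10%, the pooled rate of 1.82 per 100 patient-years falls by about 0.01-0.16, against a planned half-width of 0.24. The effect on the pooled rate is probably small; it would show more in a comparison by calendar year.

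This rests on three assumptions: that I46 corresponds to part of 427.x, as Appendix 4 suggests; that the protocol's planning rate and uniform entry are a fair scale; and that the assumed range covers the true share. The ischemic stroke row remains at most a question to the sponsor.

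**What to change.** Before programming, make the arrhythmia row of Appendix 3 equivalent in the two coding systems. Either add I46.x to the ICD-10 side, or limit the ICD-9 side to the 427 subcodes that correspond to I47-I49. State which was meant, and apply the same pair to the one-year baseline exclusion. At the same time, ask the sponsor to confirm that 433.x and 434.x are equivalent to I63.x and I66.x in the ischemic stroke row. The cost is an edit to one code row and one confirmation; no new data are needed.

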7.2 OUTCOMES

7.2.1 Primary outcomes

➤ Incidence rate of adverse events in patients with COPD treated with Tio+Olo

List of adverse events:

For acute, potentially recurrent events, including COPD exacerbations listed below, all subjects will be evaluated, regardless of whether such events occurred during the one-year baseline period.

- Respiratory tract disorders
 - 1. Nasopharyngitis
 - 2. Pneumonia
 - 3. COPD exacerbation
- Gastrointestinal disorders
 - 1. Constipation
 - 2. Diarrhoea
- Urinary disorders
 - 1. Urinary retention
 - 2. Urinary tract infection
- Immune system
 - 1. Urticaria

Statistical and Epidemiological Analysis Plan (SEAP) for Non-Interventional Studies (NIS) Template

c40431892-01 Page 10 of 38

Proprietary confidential information © 2022 Boehringer Ingelheim International GmbH or one or more of its affiliated companies

2. Rash

For chronic conditions listed below, subjects who had diagnosis of the condition during the one-year baseline period will be excluded from the incidence of adverse event analysis.

- Cardiovascular disorders
 - 1. Arrhythmia
 - 2. Myocardial ischemia
 - 3. Supraventricular tachycardia
- Ophthalmic disorders
 - 1. Glaucoma
- Serious Adverse Event (SAE)
 - 1. Nonfatal myocardial infarction
 - 2. Nonfatal stroke (hemorrhagic stroke, ischemic stroke and acute cerebrovascular disease)

Lastly, all-cause mortality, a serious adverse event, will be evaluated.

Relevant ICD codes and operational definition are provided in the Annex.

[figure not shown]
For the analysis of the primary outcome, individuals will be followed up from the index date until the earliest of the following

- 1) Outcome of interest
- 2) disenrollment;
- 3) the end of the study period;
- 4) death;
- 5) discontinuation of the index drug use as a lapse of 45 days without subsequent prescription;
- 6) adding ICS mono on top of Tio/Olo.

Statistical and Epidemiological Analysis Plan (SEAP) for Non-Interventional Studies (NIS) Template

c40431892-01 Page 11 of 38

Proprietary confidential information © 2022 Boehringer Ingelheim International GmbH or one or more of its affiliated companies

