10. DATA ANALYSIS

10.1 MAIN ANALYSIS

All variables, including patient characteristics, baseline measures, and outcomes, will be analyzed descriptively.

- For all analyses, variables will be reported as follows: Continuous variables (e.g., age) will be presented as means (with standard deviation, SD) and/or medians (with interquartile range, IQR), minimum, maximum.
- Categorical variables (e.g., sex) will be presented as absolute and relative frequencies.

We will first describe formation of the study cohort. Patient characteristics at baseline will be described using standard descriptive statistics. Absolute standardized differences (ASDs) will be used to compare the characteristics between the two groups, in which a >0.1 ASD indicates a meaningful difference.

As an objective of the study was to compare the clinical attributes of patients in each study group. The standardized difference will be used as a parameter to quantify the between-group differences for each clinical attribute. This is metric is commonly used in studies utilizing

Statistical and Epidemiological Analysis Plan (SEAP) for Non-Interventional Studies (NIS) Template

c40431892-01 Page 15 of 38

Proprietary confidential information © 2022 Boehringer Ingelheim International GmbH or one or more of its affiliated companies

secondary health data, in which a standardized difference of larger than 0.1 indicates a meaningful difference with respect to the clinical attribute between the two study groups.

For the analysis of primary outcome, the incidence rates of AEs during entire follow-up period will be calculated based on the following formula:

(Total number of patients in the Tio+Olo cohort experiencing an event of interest for the first time during the given time period) / (Total person-time at risk from current use of Tio+Olo during the given period)

[figure not shown]
Number of at-risk patients will be defined for specific adverse outcome of interest, taking into account whether it is a chronic condition for which patients with a prevalent condition are not considered at risk.

For the analysis of the primary outcome, individuals will be followed up from the index date until the earliest of the following

- 1) Outcome of interest
- 2) disenrollment;
- 3) the end of the study period;
- 4) death;
- 5) discontinuation of the index drug use as a lapse of 45 days without subsequent prescription;
- 6) adding ICS mono on top of Tio/Olo.

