ANNEX 1. ADDITIONAL INFORMATION

Table 1. Demographic and cohort entry of the Tio/Olo cohort and LAMA/LABA cohort

	Tio/Olo cohort N=xxxx		LAMA/LABA coho N=xxxx	
	N	%	N	%
Gender				
Male				
Female				
Age				
Mean, SD				
40~59				
60~79				
80+				
Calendar year of cohort entry				
2014				
2015				
2016				
2017				
2018				
2019				
Season of cohort entry date				
Spring (Mar-May)				
Summer (Jun-Aug)				
Fall (Sep-Nov)				
Winter (Dec-Feb)				

Statistical and Epidemiological Analysis Plan (SEAP) for Non-Interventional Studies (NIS) Template

c40431892-01 Page 20 of 38

Table 2. Incidence rate of adverse events in patients with COPD treated with Tio+Olo

Adverse event	No. of events	Person-Years	Incidence rate (per 100 000 person year)	95% CI
Potentially recurrent events				
Nasopharyngitis				
Pneumonia				
Moderate COPD exacerbation				
Severe COPD exacerbation				
Constipation				
Diarrhoea				
Urinary retention				
Urinary tract infection				
Urticaria				
Rash				
Incident events (no occurrence o	f corresponding	g codes during t	the 1-year baselin	ie period)
Arrhythmia				
Myocardial ischemia				
Supraventricular tachycardia				
Glaucoma				
Nonfatal myocardial infarction				
Nonfatal hemorrhagic stroke				
Nonfatal ischemic stroke				
Nonfatal Acute, but ill-				
defined, cerebrovascular				
disease				
Death				

Statistical and Epidemiological Analysis Plan (SEAP) for Non-Interventional Studies (NIS) Template

c40431892-01 Page 21 of 38

Table 3. Secondary outcome (baseline comparison between two study groups)

- ,		1			J & 1)
	Tio/Ol/	o cohort	LAM	A/LABA	
		XXXX	со	hort	Standardized
			N=	XXXX	difference
	N	%	N	%	
COPD treatments in 1 year prior to inde	ex date				
LAMA					
LABA					
ICS					
ICS+LABA free combination					
ICS+LAMA free combination					
LAMA+LABA free combination					
ICS+LAMA+LABA free combination					
ICS/LABA FDC					
LAMA/LABA FDC					
ICS/LAMA/LABA FDC					
Use of other respiratory drugs in 1 year	prior to	index			
date					
Mucolytics					
Theophylline					
Short-acting beta-agonists (SABA)					
Short-acting muscarinic antagonists					
(SAMA)					
Acute COPD exacerbation in 1 year prior	or to inde	x date			
Moderate exacerbation					
0					
1					
>=2					
Severe exacerbation					
0					
1					
>=2					
All exacerbations (Moderate +					
Severe)					
0					
1 >=2					
	c prior to	indov			
Acute COPD exacerbation in the 30 day date	s prior to	inuex			
Moderate exacerbation					
0 1					
>=2					

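### The incident myocardial ischemia row keeps at risk patients whose only ischemic heart codes at baseline are 412, 414 or I25, so its rate mixes new cases with known coronary disease

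*SAP*

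**What the plan says.** Four places in the SAP govern this outcome.

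- **SAP 7.2.1** lists "2. Myocardial ischemia" under the chronic conditions, for which "subjects who had diagnosis of the condition during the one-year baseline period will be excluded" from the incidence analysis.
- **SAP 10.1** states the principle. The number at risk is set per outcome, allowing for whether it is a "chronic condition for which patients with a prevalent condition are not considered at risk".
- **Annex 1, Table 2** puts the row under incident events. Its group header (broken in the extracted text) defines these by the absence of the corresponding codes in the 1-year baseline.
- **Appendix 3, row 6** gives the only codes for the outcome: "ICD9: 410.x, 411.x, 413.x ICD10: I20.x, I21.x, I22.x, I23.x, I24.x". The case rule is "Inpatient or outpatient (including ER visit) diagnosis", so a single code is enough.

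Appendix 4, row 2 defines baseline cardiovascular disease more widely. Its ICD-9 list includes "410-414, 425-428, 429.1", which covers 412 and 414, and its ICD-10 list includes I25.x. It requires an inpatient diagnosis or more than two outpatient diagnoses.

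**The concern.** The principle in SAP 10.1 concerns a prevalent condition, while Table 2 applies it through a code list that leaves out part of that condition. A patient followed through the whole baseline year under 414 or I25, with no code from Appendix 3 row 6, passes the screen as free of the disease. If a clinic visit after the index date is coded 413 or I20, that patient enters the numerator as incident. This is a matter of which codes are screened. It would remain with a longer look-back.

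Myocardial ischemia is one of the primary safety outcomes. The result is an absolute rate in the Tio+Olo cohort, and Protocol 11.3 says the study report goes to health authorities. A reader of the incident row would take it as the rate of newly appearing disease, when part of it may be new coding in patients already known to have coronary disease.

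**Working it through.** **1. Codes side by side**

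| Use | ICD-9 | ICD-10 |
|---|---|---|
| Event, and by Table 2 the baseline screen (Appendix 3, row 6) | 410, 411, 413 | I20–I24 |
| Ischemic heart codes within baseline cardiovascular disease (Appendix 4, row 2) | 410–414 | I20–I22, I24, I25 |
| In Appendix 4 but not screened | 412, 414 | I25 |

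The SAP prints no label for 412, 414 or I25. Reading them as known coronary disease uses their standard code meaning.

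**2. The plan's own figures.** Protocol Table 1 has no row for myocardial ischemia, so there is no stated rate to test. Its other rows do show the planned person-time: 4,000 patients × a mean of 3 years (uniform entry over 0 to 6 years) = 12,000 person-years (PY). For arrhythmia, 1.82 per 100 PY × 12,000 PY = 218.4 expected events. The 2.5% and 97.5% Poisson quantiles are 190 and 248, and dividing by 12,000 PY gives 1.583 and 2.067 per 100 PY, as printed. The other three rows reproduce in the same way. Only the 12,000 PY is carried forward, as an illustration.

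**3. Formula.** Let

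- p = share of at-risk person-time in patients with 412/414/I25 and no Appendix 3 row 6 code in the baseline year;
- r0 = rate of a first listed code in the remaining patients;
- RR = the first group's rate divided by r0.

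The planned rate is p·RR·r0 + (1 − p)·r0. Divided by r0, this gives an inflation of 1 + p(RR − 1). The share of counted cases that come from the 412/414/I25 group is p·RR / (1 − p + p·RR).

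**4. Values.** The documents give none of p, RR or r0, so every input below is an assumption.

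| p | RR | Inflation | Share of cases from the group |
|---|---|---|---|
| any | 1 | 1.00 | p |
| 5% | 2 | 1 + 0.05 × 1 = 1.05 | 0.10/1.05 = 9.5% |
| 10% | 3 | 1 + 0.10 × 2 = 1.20 | 0.30/1.20 = 25.0% |
| 10% | 5 | 1 + 0.10 × 4 = 1.40 | 0.50/1.40 = 35.7% |
| 20% | 5 | 1 + 0.20 × 4 = 1.80 | 1.00/1.80 = 55.6% |

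**5. Against sampling error.** Take r0 = 1.0 per 100 PY (assumed) and 12,000 PY.

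- **p = 10%, RR = 5.** The remaining patients give 10,800 PY and 108 events; the 412/414/I25 group gives 1,200 PY and 60 events. As planned: 168/12,000 = 1.40 per 100 PY (exact 95% CI 1.20 to 1.63). With the wider screen: 108/10,800 = 1.00 (0.82 to 1.21). The shift of 0.40 is larger than the half-width of either interval.
- **p = 5%, RR = 2.** As planned: 126 events, 1.05 (0.88 to 1.25). With the wider screen: 114 events in 11,400 PY, 1.00 (0.83 to 1.20). The shift is lost in sampling error.

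**The case against.** The strongest reply is that this is a choice of estimand. The adverse event is named myocardial ischemia, which is narrower than ischemic heart disease. Event codes and screening codes agree, so the plan follows the rule printed in Table 2. A first recorded ischemic event in a patient with known coronary disease is a legitimate safety event. The chronic label is also loose, since the same list holds nonfatal myocardial infarction and nonfatal stroke. Appendix 4, row 2 is a broad comorbidity composite (it also takes in 401–405, 441, 442 and 458), so it does not show that the SAP regards 414 as the same condition as the adverse event.

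Much of this stands. Outright removal of these patients would discard real events, and nothing here shows a coding mistake. It does not settle the matter, because SAP 10.1 speaks of the prevalent condition and the SAP nowhere says that known coronary patients are meant to remain at risk. A row labelled incident needs that stated, or the two groups shown apart.

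Two further points stand. The visible analyses compare the cohorts on baseline characteristics only, so no visible comparison of event rates is distorted, and Table 3 will report baseline cardiovascular disease. SAP 10.2 is not visible, and the protocol's ENCePP checklist places stratified and sensitivity analyses in a protocol section (9.7.2) that is also not visible. Rates split by baseline disease may already be planned there.

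**Conclusion.** The point holds for the myocardial ischemia row. On the visible text, patients with 412/414/I25 and no listed code at baseline are at risk, and a single later 413 or I20 code counts as incident, which does not match the principle in SAP 10.1. The rate is inflated if this group receives listed codes more often than the rest, and unchanged if RR = 1. On the assumed values the factor is 1.05 to 1.8; the documents support no particular figure.

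Three stronger readings are tempting and should not be drawn.

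- **That supraventricular tachycardia (SVT) has the same fault**, because its row screens only 427.0/I47.1. A first SVT in a patient with another arrhythmia can be genuinely new, and the arrhythmia row already screens all of 427.x and I47–I49.
- **That the rate is inflated several-fold.** A tripling requires RR = 1 + 2/p, which is 21 at p = 10% and 11 at p = 20%. Nothing in the documents supports such values.
- **That every patient with 414 or I25 at baseline contributes.** Those who also carry 410, 411, 413 or I20–I24 in that year are already excluded, so p is smaller than the overall 414/I25 prevalence.

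**What to change.** Keep the event codes in Appendix 3, row 6. For the incident row, screen the baseline year on any occurrence of 410–414 or I20–I25, and write that screening list into Appendix 3 separately from the event list. Add one row to Table 2 for myocardial ischemia events in known coronary disease, covering patients with baseline 412/414/I25 and no listed code, with their own events, person-years, rate and 95% CI. If SAP 10.2 already contains such a split, a cross-reference from the Table 2 row would do.

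The cost is one code range and one table row, from claims already used for Appendix 4. The new-onset row loses about a share p of its person-years and a larger share of its events, 9.5% to 55.6% in the four assumed cases with RR above 1. Those events move to the separate row, so none is lost, but the new-onset estimate rests on fewer events.
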